Diabetic foot ulceration (DFU) is a common and largely preventable complication. [1] While most of these ulcers can be treated successfully, some will persist and become infected. Ultimately, nearly one fifth of patients with infected lower-extremity diabetic ulcers will require amputation of the affected limb, resulting in staggering costs for both the patient and the healthcare system. Prevention by identifying people at higher risk is the key for better clinical management of such patients. It is not uncommon for patients suffering from diabetes to have concomitant lower extremity edema or even venous insufficiency[2-4] and they subsequently may benefit from graduated compression[5-7]. However, because of the common association of peripheral arterial disease (PAD) in patients with diabetes[8-10], most clinicians are reluctant to apply compressive dressings in fear of exacerbating the symptoms of PAD and the possible resulting gangrene[11].

Unfortunately, this area has received comparatively little attention from industry, academia, or insurance providers. A novel micro-mobile intermittent pneumatic foot compression device (AVEX Footbeat, Inc.) offers alternative means providing lower extremity compression. This device is portable and can be used in ambulatory settings providing increased venous blood and relief from concomitant lower extremity edema.

Section D: Purpose and Objectives

The purpose of this study is to conduct an observational study with N=30 patients to assess whether this micro-mobile foot compression device can help reduce lower extremity in patients with both diabetes and lower extremity edema without compromising the vascular supply.

The main purpose of this study is to determine if the device lessens edema. This study will also evaluate a new research device to see if it may help prevent diabetic foot ulcers. Additionally, it may potentially help delay progression of foot disease and produce a better quality of life by providing a better blood flow to foot and ankle.

Primary Endpoints: Reduction in lower extremity edema at 4 weeks of continuous device usage. Peripheral edema will be measured at baseline, 48 hours, 1 week and 4 weeks. Peripheral edema will be directly measured by traditional volume change assessment and indirectly by skin perfusion pressure assessment.

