Secondary Endpoints: 1) Improvement in balance and fall risk as measured at baseline and 4 weeks. 2) 48 Hours of continuous daily physical activity using a validated body worn sensor as measured at baseline and 4 weeks. 3) Gait assessment at baseline and 4 weeks.

Specific Aim and Hypothesis

Aim 1. To assess the effectiveness of a micro-mobile foot compression device that provides mild compression to help reduce peripheral edema as compared to baseline in patients with both diabetes and lower extremity edema in a four-week observational clinical trial of 30 patients.

Hypothesis 1: The micro-mobile foot compression device will result in edema reduction when compared to baseline peripheral edema for the study population.

Aim 2. To assess the effect of micro-mobile foot compression device on the macro and micro lower extremity circulation as measured by Ankle Brachial Index (ABI) and Skin Perfusion Pressure (SPP) Measurements.

Hypothesis 2: The micro-mobile foot compression device will help improve macro and micro- circulation in the lower extremity of patients with diabetes and lower extremity edema as compared to baseline. We expect to see positive changes in ABI and SPP measurements.

Aim 3. To assess the effect micro-mobile foot compression device on the quality of life quantified using the validated, international quality of life assessment survey SF12, fear of falling quantified by FES-I, and risk of falling assessment quantified by gait, balance and spontaneous daily physical activity of patients with diabetes and lower extremity edema.

Hypothesis 3. The micro-mobile foot compression device will improve the quality of life, lower the risk of falling, lower fear of falling, and improve activity level of patients as compared to baseline assessments.

Section E: Protocol Risks/Subjects

E1. Risk Category

Category 2: Research involving greater than minimal risk, but presenting the prospect of direct benefit to the individual subjects.

E2. Subjects

Gender:

Both

Age:

Adult (18-64 yrs), Geriatric (65+ yrs)

Ethnicity:

All Ethnicities

Primary Language:

English, Spanish

Groups to be recruited will include:

Patients

Which if any of the following vulnerable populations will be recruited as subjects?

Vulnerable populations require special protections. How will you obtain informed consent, protect subject confidentiality, and prevent undue coercion?

E3. Pregnant woman/fetus

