Will pregnant women and/or fetuses (as described in 45 CFR 46 Subpart B) be enrolled in the research?

No

E4. Neonates

Will neonates of uncertain viability or nonviable neonates (as described in 45 CFR 46 Subpart B) be enrolled in the research?

No

E5. Children

Will children be enrolled in the research?

No

Section F: Design/Procedure

F1. Design

Select one category that most adequately describes your research:

c) Pilot

Discuss the research design including but not limited to such issues as: probability of group assignment, potential for subject to be randomized to placebo group, use of control subjects, etc.

In this proof of concept, intent to treat trial, 30 consecutive patients with diabetes and lower extremity edema will be recruited from the outpatient clinic at Baylor College of Medicine. Patients will be consented per the local Institutional Review Board's guidelines and approval for this study.

Inclusion Criteria:

a) Males or females age 18-90 years old with history of type 1 or 2 diabetes and the ability and willingness to provide Informed consent b) Patients at risk of developing diabetic foot ulcers c) Patient is willing to participate in all procedures and follow up evaluations necessary to complete the study. d) Patients who have undergone lower extremity surgery / amputation may be enrolled into the study at the clinical judgment of the Investigator

Exclusion Criteria:

a) Patients with severe peripheral vascular disease (ABI or ankle brachial systolic pressure index <0.5) b) Patients with diabetic foot ulcers in the plantar foot region c) Patients with active wound infection, or untreated osteomyelitis d) Patients currently on immunosuppressive drugs. e) Pregnant or breastfeeding females. (standard urine pregnancy done on women during physical exam procedures) f) Acute fractures of the foot g) Acute heart failure h) Participation in an interventional Study within the last 30 days i) Non-ambulatory or unable to stand without help or walk a distance of at least 6 feet without assistance. k) Patients with major foot amputation. j) Patients who are unable or unwilling to participate in all procedures and follow up evaluations h) Patients with major foot deformities which won't fit in the diabetic shoes

F2. Procedure

Following is a summary of study procedures:

Study Day 0 (initiation), Visit 1 The following baseline values will be assessed and documented.

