Statistical Analysis - This study includes three hypotheses. To examine whether the proposed micro-mobile foot compression device will result in a edema reduction compared to the baseline (H1), we will use ANOVA and Fisher's exact tests for intra-subject rate of edema reduction using the outcome explained before. Multivariate and multiple linear regression test will be used for testing the effects of confounding factors including age, gender, BMI, foot insensitivity, etc. Additional, paired t-test will be used to examine whether amount of edema reduction at the end of study is significant compared to baseline. We will use Pearson correlation of coefficient and Fisher's exact tests to examine whether severity of neuropathy has any significant association with the rate of edema reduction. Finally, we will use multiple linear regression model to examine whether subject's level of activity, BMI, ABI, Skin perfusion pressure, and micro-mobile foot compression device are independent predictors for the rate of edema reduction.

To examine whether the proposed sock will help improve macro and micro-circulation in the lower extremity of patients (H2), we will use the similar analytical plan explained above by considering change in Skin perfusion pressure and ABI as dependent variables. For identifying the predictors, we will use multiple linear regression model and Anova (n-way). The independent variables will be severity of neuropathy quantified using Semmes Weinstein Monofilament, the level of activity, BMI, and age.

To examine whether the proposed socks will improve the activity level and quality of life (H3), we will use ANOVA multivariate test. The dependent variables will be number of total steps per day, duration of walking and standing, duration of longest episode of walking (i.e. continuous walking without stop), number of walking episode, duration of sit-to-stand and stand-to-sit postural transition, and SF12. We will use multiple linear regression model and multi-variant test to examine the effect of confounding parameters such as weather condition, BMI, age, etc.

Section H: Potential Risks/Discomforts

H1. Potential Risks/Discomforts

Describe and assess any potential risks/discomforts; (physical, psychological, social, legal, or other) and assess the likelihood and seriousness of such risks:

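### Perfusion safety in patients with PAD is part of the rationale, but H2 reports ABI and SPP change only over all patients, so a fall in PAD patients can be diluted; a descriptive split by baseline arterial status would show it

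*Combined protocol and SAP*

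**What the plan says.** The background, before Section D, gives the clinical obstacle: "most clinicians are reluctant to apply compressive dressings in fear of exacerbating the symptoms of PAD and the possible resulting gangrene". Section D then sets the purpose as reducing edema "in patients with both diabetes and lower extremity edema without compromising the vascular supply". The same section names edema reduction as the main purpose.

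Entry is in Section F1. The inclusion criteria ask for diabetes and for "Patients at risk of developing diabetic foot ulcers"; none asks for PAD. Exclusion a) removes "Patients with severe peripheral vascular disease (ABI or ankle brachial systolic pressure index <0.5". Recruitment is not stratified: "30 consecutive patients with diabetes and lower extremity edema will be recruited from the outpatient clinic".

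Hypothesis 2 is stated for the whole population: the device "will help improve macro and micro- circulation in the lower extremity of patients with diabetes and lower extremity edema as compared to baseline". For its analysis, Section G2 says "we will use the similar analytical plan explained above by considering change in Skin perfusion pressure and ABI as dependent variables". After a sentence on identifying predictors, it adds: "The independent variables will be severity of neuropathy quantified using Semmes Weinstein Monofilament, the level of activity, BMI, and age". PAD status, baseline ABI and baseline SPP are not in that list. ABI and SPP do appear as predictors in G2, but in the H1 model for edema reduction.

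Section F2 has ABI measured in both limbs and SPP in all patients at Visit 1. The medical history taken there includes lower-extremity bypass and angioplasty. The 4-week visit repeats similar assessments.

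**The concern.** The patients in whom compression is feared are those with arterial disease. Their number in the sample is left to chance, and H2 gives one average change over everyone. If perfusion falls in PAD patients and is stable or rises in the rest, the average lies between the two and is pulled towards the larger group. The pooled test may then show nothing, or even an improvement.

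What is at stake is the part of the purpose about vascular supply. A pooled result close to zero is compatible with no harm in anyone and also with harm in a minority offset by the majority, and the planned output does not separate the two. The data that could do so are already collected.

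**Working it through.** **No figure to reproduce.** Section G1 justifies the sample size as a pilot and gives no SD, effect, PAD share, alpha or power. Everything numerical below is an assumption made to show the mechanism and its range.

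**Inputs.** n = 30 (Sections D and F1) or 50 (Section G1); the two should be reconciled. Assumed: k patients with PAD; change in units of its within-group SD; PAD patients fall by L; the others change by g; two-sided 5% one-sample t-test on change, counting significant declines only.

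**Pooled mean.** Pooled mean = (−k·L + (n − k)·g)/n. With n = 30, k = 9, L = 1, g = 0 it is −9/30 = −0.30 SD. If the SD of ABI change were 0.10, a fall of 0.10 in the PAD patients would appear as −0.03 overall.

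**Detection.** PAD-only: noncentral t with k − 1 degrees of freedom and noncentrality −L·√k. Pooled: simulation with k fixed. With g = 0:

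| n | PAD patients | Fall L | Pooled | PAD-only |
|---|---|---|---|---|
| 30 | 9 | 1.0 SD | 28% | 75% |
| 30 | 9 | 0.8 SD | about 20% | 56% |
| 30 | 9 | 0.5 SD | 11% | 26% |
| 30 | 9 | 0.3 SD | 7% | 12% |
| 30 | 6 | 1.0 SD | 15% | 51% |
| 30 | 15 | 1.0 SD | 67% | 95% |
| 50 | 15 | 1.0 SD | 47% | 95% |

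Hand check of the first row: the pooled SD is about √(1 + (30/29)·0.3·0.7·1²) = 1.10, so the expected t is about −0.30·√30/1.10 = −1.49, well short of the critical value of about 2.05.

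**If the others improve, as H2 expects.** With n = 30, k = 6, L = 0.8 and g = 0.2, the pooled mean is (−6·0.8 + 24·0.2)/30 = 0. With g = 0.5 it is (−4.8 + 12)/30 = +0.24 SD, and the pooled test shows a significant improvement about 17% to 20% of the time while the PAD patients lose 0.8 SD.

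**Precision of a split.** The 95% CI half-width in the PAD group is t(0.975, k − 1)/√k: 0.77 SD for 9 patients, 1.05 SD for 6, 2.48 SD for 3. With 3 patients even a 1 SD fall is detected only 18% of the time. The split can be descriptive only.

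**A trap in the obvious split.** Grouping on a single baseline ABI and then reporting ABI change from that same reading, without a control group, brings regression to the mean. Illustration: mean ABI 1.0, change SD 0.10 that is all measurement noise (0.10/√2 = 0.071 per reading), true between-patient SD s, low group defined as a reading below 0.9. The 0.9 is an arithmetic device, not a proposed limit. With V = s² + 0.005 and a = −0.10/√V, the expected rise with no true effect is (0.005/√V)·φ(a)/Φ(a).

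- s = 0.15: V = 0.0275, a = −0.603, rise = (0.005/0.1658)·1.217 = +0.037.
- s = 0.10 and s = 0.20 give +0.056 and +0.026.

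The spurious rise works against the decline being looked for. For a true fall of 0.10 in 9 patients, detection drops from 75% to about 24%, 41% and 51% at s = 0.10, 0.15 and 0.20.

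**The case against.** Edema is the declared main purpose, and the target population is consistently patients with diabetes and edema. The PAD sentence is background on why conventional dressings are avoided, and no aim, hypothesis or endpoint claims safety in PAD. A reader might infer that the trial was set up to answer the PAD question, or that it plans to present a pooled null result as support for compression in PAD. The documents support neither reading. What stands is narrower: vascular supply is in the purpose sentence, Aim 2 tests circulation, and nothing in the plan stops the pooled result from being applied to PAD patients.

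A reader might also infer that arterial status is shut out of H2. That is too strong. H2 borrows a plan similar to H1's, whose regression includes ABI and SPP, and the four-variable list may describe only the predictor step. Read generously, though, this adds at most a main effect. The coefficient would describe how change differs with arterial status; the plan would still not commit to reporting the change within PAD patients with its interval. Baseline ABI as a predictor of ABI change also carries the regression to the mean shown above.

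Nor do the documents support assuming that patients without PAD have little at stake or little room to improve; H2 expects gains across the population.

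Finally, this is a proof-of-concept pilot and any PAD group will be small. That is a fair limit on what a split can show. It argues for description without a formal test, and for a conclusion no wider than the data.

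**Conclusion.** The point holds as a gap in reporting for a non-primary aim. The plan has no output that separates perfusion change in patients with PAD from change in the rest, although PAD is the stated source of concern and the baseline measurements are planned. The direction of the effect is certain: averaging dilutes a fall confined to one group whenever that group is less than the whole sample and the others do not fall.

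The size is not known. It depends on the PAD share, the effect and the change in the others, none of which is in the documents. The wide gap of 28% against 75% needs a fall of a full SD in 9 of 30 patients; at 0.3 SD both approaches are weak (7% against 12%), and a split would seldom settle the matter. Patients with ABI below 0.5 are outside the study altogether, so no analysis can speak to severe PAD. H1 is unaffected. This is a cheap improvement and does not undermine the trial.

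**What to change.** Amend Section G2 for H2 before any follow-up data are seen:

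- Define baseline arterial status in advance, and report ABI change and SPP change by that status with the number of patients and 95% CIs. Label this a planned descriptive analysis.
- Do not classify and measure change on the same single reading. Either classify by documented history of PAD or revascularisation, or use baseline SPP groups for ABI change and baseline ABI groups for SPP change. State the regression-to-the-mean caveat that remains.
- Limit any conclusion about vascular supply to the groups whose own interval supports it. State that severe PAD (ABI below 0.5) was not studied. If few PAD patients enrol, state that the PAD question is not answered.

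The cost is some wording and one table, from data already planned. The downsides are wide intervals, residual regression to the mean in an uncontrolled comparison, and probably a narrower conclusion. The group-specific SDs and the PAD share would also help to size the larger trial that Section G1 foresees.

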Other assessments: Other relevant assessments are Demographic/Health questionnaire, the Mini-Metal State Exam, the mobility-tiredness scale, Barthel Index, Depression Scale, fear of falling (Short-Falls Efficacy Scale – International)[25], quality of life (SF-12 Health Survey)[26], Fried Frailty Criteria, Foot Questionnaire, Pain Assessment, Fall Log and Contact Agreement, Physical activity log, follow-up questionnaire, and Shoe-fit test

AVEX insole: The AVEX insole will be given to the subject. The research personnel will adjust the clutching reel (BOA technology) in order to ensure a comfortable shoe fit. The research personnel will also provide device education to the subject and will answer any questions which may arise.

Study Day 1, Visit 2 48-hour follow up: All participants will be asked to return to clinic approximately 48 hours after visit 1. In this visit, (1) any adverse events will be assessed; (2) activity measurement (body sensor) will be returned; (3) AVEX insole data will be downloaded to ensure operability and patient compliance; and (4) further device education will be provided in case any issues have risen

Study Day 2, Visit 3 1-week follow-up: All participants will be asked to return to clinic approximately 1 week after visit 1. In this visit, (1) any adverse events will be assessed; and (2) AVEX data download to ensure operability and patient compliance. Device education will be provided if needed. The subject will be asked to return the device at their next visit. Similar assessments performed during visit 1 may be performed again during this visit.

Study Day 3, Visit 4 4-week follow-up: All participants will be asked to return to clinic approximately 4 weeks after visit 1. In this visit, outcome assessment using similar assessments described for Study Day 0 will be performed. In addition, benefit and user-friendliness of the AVEX insoles and Boa Technology 'Clutch Reel' will be assessed using a questionnaire. The subject will return the device back to the research personnel.

Patients will be asked to wear a comfortable shirt which holds a small activity monitor (PAMSys) for a period of 48 Hours (2 days). Patients will be requested to return this device via a pre-paid FEDEX envelope

Study Day 4, Visit 5 Three month follow-up: All participants will be contacted by the study coordinator approximately three months post the last study visit (Visit 4) to document potential incident of diabetic foot ulcer or falls.

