The AVEX Footbeat insole is an investigational device, which has been designed to enhance blood flow to lower extremities via a Micro-Mobile Foot Compression Device. The compression component applied pressure under your foot arch. We will perform initial screening to ensure the safety of the device. But as any new insole, there is some risk that the insole caused some discomfort or cause development of foot ulcers. It is important to notify us if you feel discomfort on wearing the insoles or if you feel excessive pressure to your feet because of wearing the AVEX Footbeat insole.

The study device and technology is completely non-invasive, safe, non-toxic and non-ionizing. The potential risks to you are minimal. However, like any battery powered systems, there is a minimum risk of sensor malfunctioning. In addition, the study devices are not waterproof, and although they use a low powered battery (similar to a cell-phone battery), in order to avoid any risk of shock the monitor should not be submerged or saturated with fluids during operations or cleaning.

You must be willing to charge device battery daily. Otherwise they will not receive benefit from compression component during treatment.

The assessments described above are expected to be minimal risk and probability and magnitude of harm or discomfort anticipated in the research are not greater in and of themselves than those ordinarily encountered in daily life or during the performance of routine physical or psychological examinations or tests.

Please note that there is also the possibility for loss of confidentiality. The PI and the research team will minimize the possibility of for loss of confidentiality by keeping all the physical data locked in cabinets only accessible to the research team. The electronic data will be kept on network password protected institutional computers. And, subject PHI will be coded as much as possible to minimize the potential for loss of confidentiality.

H2. Data and safety monitoring plan

Do the study activities impart greater than minimal risk to subjects?

No

H3. Coordination of information among sites for multi-site research

Is the BCM Principal Investigator acting as the SPONSOR-INVESTIGATOR for this multi-site research?

No or Not Applicable

Is BCM the COORDINATING CENTER for this multi-site research?

No or Not Applicable

Section I: Potential Benefits

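### The primary endpoint is worded on-treatment in a trial declared intent to treat, and the paired t-test by default drops patients without a 4-week value, so the single-arm edema reduction may be overstated

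*Combined protocol and SAP*

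**What the plan says.** Three places describe who the result is about.

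- Section D, Primary Endpoints: "Reduction in lower extremity edema at 4 weeks of continuous device usage". Edema is to be measured at baseline, 48 hours, 1 week and 4 weeks.
- F1, Design: "In this proof of concept, intent to treat trial".
- Specific Aim and Hypothesis, Hypothesis 1: "The micro-mobile foot compression device will result in edema reduction when compared to baseline peripheral edema for the study population".

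For Hypothesis 1, G2 starts with "we will use ANOVA and Fisher's exact tests for intra-subject rate of edema reduction using the outcome explained before", goes on to regression for confounders, and then adds that a "paired t-test will be used to examine whether amount of edema reduction at the end of study is significant compared to baseline". The form asks which analysis is primary; the answer names none.

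On device use, F2 says at the 48-hour visit that "AVEX insole data will be downloaded to ensure operability and patient compliance", and lists a similar download at 1 week. G2 gives these data no role. The risk section (H1, Potential Risks/Discomforts) says "You must be willing to charge device battery daily", and adds that a patient who does not will get no compression benefit.

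The documents do not define an analysis set or continuous usage, and give no rule for non-use, early withdrawal or a missing 4-week edema value. Section L foresees patients who do not complete, since it pays them for the visits they made.

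**The concern.** The endpoint wording points to patients who kept using the device. The intent-to-treat label and Hypothesis 1 point to everyone enrolled. These are different quantities, and the plan does not say which one it will estimate.

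The paired t-test is the only listed test that is explicitly end of study against baseline. It needs both values, so with no missing-data rule a patient who has left by 4 weeks contributes nothing. The documents give reasons why leavers might have had less benefit: the risk section mentions discomfort and possible ulcers from the insole, and no compression benefit if it is not charged.

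With no control arm, the mean change is the whole result, and no comparator with similar losses can offset a selective one. G1 says the results will be used to size a larger superiority trial, so an inflated change could be carried into that calculation.

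**Working it through.** **The plan's own figure.** There is none to reproduce. The sample size (30 in Section D and F1, 50 in G1) comes with no alpha, power, effect size, standard deviation or dropout rate. The ratios below do not depend on which N is right.

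**Inputs, all assumed because the documents give no rates**
- d: share of patients who leave before 4 weeks (10, 20, 30%).
- r: leavers' mean reduction relative to stayers', whose mean is set to 1.

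**Step 1. Patients who leave.** The paired test estimates the stayers' mean, 1. The all-enrolled mean is (1 − d) + d·r. The ratio of the two is 1 / [(1 − d) + d·r].

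For example, with d = 0.20 and r = 0 the all-enrolled mean is 0.80 and the ratio is 1/0.80 = 1.25. With d = 0.20 and r = 0.5 it is 1/(0.80 + 0.10) = 1/0.90 = 1.11.

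| Leavers' reduction relative to stayers (r) | d = 10% | d = 20% | d = 30% |
|---|---|---|---|
| 0 (no change) | 1.11 | 1.25 | 1.43 |
| 0.5 (half) | 1.05 | 1.11 | 1.18 |
| 1 (the same) | 1.00 | 1.00 | 1.00 |
| 1.5 (improved more) | 0.95 | 0.91 | 0.87 |

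The first row is not a strict bound: it would be exceeded if leavers' edema worsened (r below 0).

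**Step 2. Non-use is not the same as leaving.** Now let d be the share of non-users, all with no change, and let only a fraction q of them leave. The patients seen at 4 weeks have mean (1 − d) / (1 − d·q), the all-enrolled mean is 1 − d, and the ratio is 1 / (1 − d·q).

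| Fraction of non-users who leave (q) | d = 20% | d = 30% |
|---|---|---|
| 0 | 1.00 | 1.00 |
| 25% | 1.05 | 1.08 |
| 50% | 1.11 | 1.18 |
| 100% | 1.25 | 1.43 |

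If all non-users attend at 4 weeks and are analysed, there is no bias.

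**Step 3. Effect on the later trial.** Required sample size varies with 1/effect². If the pilot's mean change were taken as the effect, with the same standard deviation, the later trial would be sized at (1/ratio)² of what is needed. For r = 0 this is 0.90² = 81%, 0.80² = 64% and 0.70² = 49%. For r = 0.5 it is 0.95² = 90%, 0.90² = 81% and 0.85² = 72%. The later trial is to compare with standard care, so this carries over only if the pilot change is used as the expected difference.

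**Step 4. Can the planned intermediate values help?** Section D puts edema at 48 hours and 1 week. The F2 list for the 48-hour visit has no edema measurement, and at 1 week F2 makes repeat assessments optional. If they are not taken, an early leaver has a baseline value only, and no model can recover that patient's change from the patient's own data.

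**The case against.** A reader might infer that the plan restricts the analysis to completers or to users. It does not say so. The exclusion of patients without a 4-week value follows only from how a paired test works when no missing-data rule is given. That test is listed as additional, after ANOVA and Fisher's exact tests. Fisher's test could count a patient with no final value as not reduced, although the plan does not say that it will.

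A reader might also infer that a patient who stops using the device leaves the analysis. The documents do not support this. F2 asks all participants back at 4 weeks with no condition on use, the inclusion criteria require willingness to complete follow-up, Section L pays per completed visit, and the downloads are there to check function and compliance. A non-user who attends is in the paired test, and a paired test on all enrolled patients with complete data would respect intent to treat.

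Nor do the documents show that the reduction will be overstated. That needs leavers to have done worse than stayers, and no dropout or adherence rate is given. The phrase about continuous usage can even be read as the intended exposure period, since no wear threshold is attached to it.

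These points limit the concern to a conditional one, and they make the first row of the Step 1 table the severe end of the scenarios shown. They do not settle which quantity is primary or what happens to a patient without a 4-week value. It is fair to add that this is a pilot. But its stated use is to size a later trial, and that depends on a change estimated in a defined group.

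**Conclusion.** The concern holds in conditional form. The endpoint wording and the intent-to-treat declaration point to different quantities, nothing reconciles them, and the paired t-test falls back on complete cases. The mean reduction may therefore be overstated if leavers did worse than stayers.

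The size rests on assumed dropout of 10, 20 or 30%: 11, 25 or 43% if leavers had no change, and 5, 11 or 18% if they had half the stayers' reduction. It is zero if they had the same reduction, or if non-users attend and are analysed. It reverses if leavers improved more: at one and a half times the stayers' reduction, the test understates by 5, 9 or 13%. The documents cannot say which case applies.

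**What to change.** 1. State that the primary analysis includes every patient issued an insole with a baseline edema value, whatever the recorded use, and that 4-week edema is measured and analysed regardless of use.
2. Name one primary test: the baseline-to-4-week contrast from a repeated-measures mixed model over the four times in Section D. Use one edema measure throughout, since F2 allows either circumference or water displacement.
3. Reconcile F2 with Section D so that edema measurement at the 48-hour and 1-week visits is firm. Otherwise early leavers add almost nothing to the model.
4. The mixed model assumes data missing at random, which may fail if patients leave because of non-use or discomfort. Add a sensitivity analysis that sets missing 4-week values to no change.
5. Define continuous usage from the insole download data and report the change in those users as secondary. F2 lists downloads at 48 hours and 1 week but only device return at 4 weeks, so a download at return should be listed.

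This needs no extra patients or visits. The cost is edema measurement at two visits already scheduled, and a headline reduction that may be smaller: 10, 20 or 30% below the completer mean in the no-change scenarios. It is a cheap improvement.
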